### **4.3 Gender/Minority/Pediatric Inclusion for Research**

*Men, women, and minorities will all be included. There will be no pediatric patients included in this research*

### **4.4 Subject Recruitment and Screening**

*138 adult patients will be recruited from the outpatient surgical clinics of the Pancreas, Biliary and Related Cancer Center. Investigators (surgeons) will offer enrollment at the time of consent for pancreaticoduodenectomy.*

### **4.5 Early Withdrawal of Subjects**

#### **4.5.1 When and How to Withdraw Subjects**

A subject may withdraw from the study at any time by contacting any of the physician researchers and making their wishes known

#### 4.5.2 Data Collection and Follow-up for Withdrawn Subjects

Data will be used for the purposes of the observation portion of the study up to the point of their withdrawal, any subsequent data will not be collected.

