**7.3 Subject Population(s) for Analysis**

**Primary Analysis Population:** All randomized patients will be analyzed as randomized in an intention to treat manner. We expect length of stay to be complete for all patients. Any subjects missing length of stay data will be excluded from all analyses. Subjects without data for a particular secondary outcome will be excluded from the analysis of that outcome.

As-treated Population: Supplemental analysis may be considered analyzing patients “as-treated” if it is determined that more than 5% of subjects were not treated as randomized.

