### ***Post-study Adverse Event***

All unresolved adverse events should be followed by the investigator until the events are resolved, the subject is lost to follow-up, or the adverse event is otherwise explained. At the last scheduled visit, the investigator should instruct each subject to report any subsequent event(s) that the subject, or the subject's personal physician, believes might reasonably be related to the interventions in this study. The investigator should notify the IRB of any death or adverse event occurring at any time after a subject has discontinued or terminated study participation that may reasonably be related to the study interventions.

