## **9.0 DATA HANDLING AND RECORD KEEPING**

### **9.1 Confidentiality**

Information about study subjects will be kept confidential and managed according to the requirements of the Health Insurance Portability and Accountability Act of 1996 (HIPAA). Those regulations require a signed subject authorization informing the subject of the following:

- What protected health information (PHI) will be collected from subjects in this study
- Who will have access to that information and why
- Who will use or disclose that information
- The rights of a research subject to revoke their authorization for use of their PHI.

In the event that a subject revokes authorization to collect or use PHI, the investigator, by regulation, retains the ability to use all information collected prior to the revocation of subject authorization. For subjects that have revoked authorization to collect or use PHI, attempts should be made to obtain permission to collect at least vital status (i.e. that the subject is alive) at the end of their scheduled study period.

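### Section 4.5.2 stops all data collection when a subject withdraws from the study, so with the exclusions in 7.3 later readmissions and complications drop out of the intention-to-treat and safety comparisons

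*Combined protocol and SAP*

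**What the plan says.** Section 4.5.1 describes a single act of withdrawal: "A subject may withdraw from the study at any time by contacting any of the physician researchers and making their wishes known". Section 4.5.2 gives its consequence: data are used "up to the point of their withdrawal, any subsequent data will not be collected".

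Four other places bear on this, and section 4.5 refers to none of them.

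- **7.3, analysis population:** "All randomized patients will be analyzed as randomized in an intention to treat manner". It also provides for a supplemental as-treated analysis if more than 5% of subjects were not treated as randomized.
- **7.3, missing data:** "Any subjects missing length of stay data will be excluded from all analyses", and "Subjects without data for a particular secondary outcome will be excluded from the analysis of that outcome". No sensitivity analysis for missing outcomes is described.
- **8.1, Post-study Adverse Event:** the investigator is to notify the IRB of "any death or adverse event occurring at any time after a subject has discontinued or terminated study participation", where it may reasonably be related to the study interventions.
- **9.1:** for subjects who revoke authorization to use PHI, earlier information is retained and "attempts should be made to obtain permission to collect at least vital status".

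The Safety part of 7.2 makes hospital readmission the primary safety outcome. Section 8.1 runs adverse event reporting to 90 days after the operation, or to the end of the index stay if that is longer.

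**The concern.** An intention-to-treat comparison needs outcomes on everyone randomized, including those who stop taking part. Section 4.5.2 rules out collecting them after withdrawal, and 7.3 then leaves those patients out. What remains is a complete-case analysis under an intention-to-treat label.

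The exposure is mainly on the harm side. Readmission can occur only after discharge, and many complications appear after discharge too. The stated objective is a shorter stay without an increase in complications or readmissions, so these are the outcomes on which the safety half of the claim rests. The trial is unblinded, and the added physical therapy, the diet and the phone contact are listed for the intervention arm. Withdrawal could therefore differ by arm and be related to a poor recovery. If it is, the 5-day arm would look safer than it is, both in the final comparison and in the Bayesian rule meant to stop the trial for excess readmissions.

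**Working it through.** **1. The plan's own safety table.** Inputs from 7.2 (Safety): priors Beta(0.2, 0.8) for the 5-day arm and Beta(15, 85) for control; stop if Pr(π_5day − π_control > 0.05) > 0.9; 36 per arm at the interim. With r readmissions among n patients, the posteriors are Beta(0.2 + r₅, 0.8 + n₅ − r₅) and Beta(15 + r_c, 85 + n_c − r_c). The probability is the integral over the control rate of its posterior density times the chance that the 5-day rate exceeds it by more than 0.05. The smallest 5-day counts that stop the study are 10, 11, 12 and 13 for 1–2, 3–5, 6–8 and 9–12 control readmissions. All match the table.

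**2. One unseen readmission at the threshold.** Control is 5/36 throughout.

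| 5-day arm as seen by the rule | Posterior probability | Decision |
|---|---|---|
| 11/36, all outcomes known | 0.910 | stop |
| 10/35, one readmitted patient excluded | 0.860 | continue |
| 10/36, same patient counted as not readmitted | 0.841 | continue |
| 9/34, two readmitted patients excluded | 0.791 | continue |

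**3. How far the illustration reaches.** One step above the threshold it fails: 12/36 less one readmitted patient is 11/35, posterior 0.923, still stop. Even on the threshold, excluding one readmitted patient does not reverse the decision with 3, 6 or 9 control readmissions (0.903, 0.907, 0.912). With a control rate of 15%, the chance that the interim lands exactly on a threshold is 0.7%, 3.8%, 9.3% or 13.3% for true 5-day rates of 15%, 20%, 25% or 30%. The rule is also re-applied every 12 patients after the interim.

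**4. Bias under assumed withdrawal.** The plan gives no withdrawal rate, so this step is assumption. Take true readmission rates of 25% (5-day) and 15% (control), a 10-point excess, with withdrawal only in the 5-day arm. Let w be the fraction withdrawn before readmission could be recorded and q the readmission rate among them. The observed 5-day rate is (0.25 − w·q)/(1 − w). For w = 0.05 and q = 0.50 this is (0.25 − 0.025)/0.95 = 0.237, a difference of 8.7 points.

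| w | Observed difference, q = 50% | Observed difference, q = 75% | Chance of interim safety stop, q = 50% / 75% |
|---|---|---|---|
| 2% | 9.5 points | 9.0 points | 21.5% / 19.5% |
| 5% | 8.7 points | 7.4 points | 17% / 13% |
| 10% | 7.2 points | 4.4 points | 13% / 6% |

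With full data the chance of an interim stop is 23%. If q = 25%, so that withdrawal is unrelated to readmission, the difference stays at 10 points and there is no bias.

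**5. Primary endpoint.** Discharge by POD 5 is settled on POD 5, so only earlier withdrawal leaves it unknown. A borderline example: 16/71 against 7/71 gives Fisher p = 0.067. Excluding one intervention patient who would not have been discharged by POD 5 gives 16/70 against 7/71 and p = 0.042, which is below the final bound of 0.04553 in 7.2.

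**The case against.** Two stronger readings are tempting, and the documents support neither.

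A reader might infer that a patient who only wants to stop the accelerated pathway is handled like one who refuses use of records. But 4.5.1 concerns withdrawal from the study, and nothing says that declining the therapy or the diet counts as that. Section 7.3 expects some patients not to be treated as randomized and keeps them in their assigned arm. Section 9.1 deals separately with revoked authorization. The distinctions exist in the document; section 4.5 does not draw or link them.

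A reader might also infer that deaths after withdrawal are simply lost. Section 8.1 sends related later deaths and events to the IRB, and 9.1 seeks permission for vital status after revocation. These cover part of the gap. Neither turns the events into trial outcome data, and 9.1 applies only to those who revoke authorization. Nor is either a flat contradiction of 4.5.2, since notifying the IRB and asking permission can coexist with a default of no further collection. The substantive tension is with intention to treat.

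The defence can add that the interim example was placed on the threshold, that study-specific contact after discharge is limited to calls on the first two days so formal withdrawal may be rare, and that informative withdrawal is assumed. All of that stands, and it limits the claim about size. It does not remove the instruction to stop collecting, which staff would follow when a subject withdraws.

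**Conclusion.** The point holds as a defect in section 4.5 and its missing links to 7.3, 8.1 and 9.1. Followed as written, 4.5.2 and the exclusions in 7.3 remove readmissions and complications after withdrawal from comparisons described as intention to treat, in an unblinded trial whose primary safety outcome is readmission.

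Bias follows only if withdrawal differs by arm and is related to recovery. Its size cannot be read from the plan. Under the assumed 5% to 10% informative withdrawal in the 5-day arm, a true 10-point excess would appear as 8.7 down to 4.4 points, and the chance of an interim safety stop would fall from 23% to between 17% and 6%. The change from 0.910 to 0.860 illustrates a case on the threshold; it is not a general property of the rule. The primary endpoint is only narrowly exposed. The plan should be amended, but the documents do not show that the trial's results will be biased.

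**What to change.** Amend 4.5.1 and 4.5.2 to define two levels of withdrawal.

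1. **The subject stops the pathway or the study contacts.** The subject stays in the assigned arm. Discharge date, readmission, complications and death are still collected from records and routine visits to 90 days.
2. **The subject refuses record use or revokes authorization.** Collection stops, earlier data are kept, and vital status is sought as in 9.1.

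Record the level, date and reason of each withdrawal by arm. Align 7.3 and 8.1 with these definitions, and add to 7.3 a sensitivity analysis for outcomes that remain missing.

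The cost is small. Section 8.5.1 already relies on chart review and on office visits up to 90 days. The consent form must cover continued record review after a subject stops taking part; it was not available for this review, so it may already do so. Readmissions at other hospitals may still be missed, because the documents do not say that they would appear in the chart.

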### **5.0 STUDY DRUG/THERAPY**

#### **5.1 Description**

1. Outpatient office: consent is obtained at the time of procedural consent during preoperative visit
2. Patients get standard preoperative, anesthetic, and operative protocols.
3. Randomization occurs at the end of the case when inclusion/exclusion criteria met.
4. The control arm follows the standard 7 day pathway
5. Care for the intervention arm is focused on seven specific interventions:
  - a. All patients are volume restricted in the perioperative period.
  - b. More rapidly leaving the ICU setting: Transfer from the ICU to floor directly following review of AM labs on POD 1
  - c. More restful night sleep, 8 hour undisturbed period for patients recovering without apparent complication: routine lab draws starting POD 2 done at 6 am (rather than 1 am), midnight nursing rounds for vital signs are adjusted to 10 pm.
  - d. Early mobilization and enhanced physical therapy: formalized physical therapy protocol emphasizing early, frequent ambulation and mandated evaluation in the gym on POD 4 and 5. Physical therapy BID beginning POD 3 (may need adjustment to POD 4 or 5 pending PT staffing resource review)
  - e. Dietary modification: anticipated discharge with patients on 2/3rds liquid diet with dietary guidelines provided
  - f. Increased, and standardized, phone contact by nurse practitioner on first two days following hospital discharge.
6. Both groups: MO/RT referrals made on POD4, routine post-operative drain amylase studies POD 3, objective PT score for all patients on POD 5 (based on % of baseline timed get up and go), Attending survey to be completed POD 5 documenting readiness for discharge and rationale, discharge is at the discretion of the attending surgeon, routine drain amylase prior to removal to facilitate early decisions on drain removal v. anticipated discharge with drain in place.

#### **5.2 Treatment Regimen**

N/A, plans as described above

#### **5.3 Risks**

The major risks for this research are the development of postoperative complications in the outpatient setting, where identification of these complications may be delayed. Other risks to these patients that are not present in our

standard 7 day discharge patient includes the the risk of fall due to early mobilization with physical therapy, and the potential for dehydration if patients are not able to tolerate adequate oral intake to maintain hydration at home following discharge. Specific measures to minimize these risks are detailed in the next question. Additional risks include violation of loss of confidentiality or violations in protecting personal health information.

The risk of a delayed diagnosis of postoperative complications will be mitigated with increased outpatient communication including daily phone calls and liberalized use of visiting nursing services and outpatient physical therapy. The risk of falls due to early mobilization will be mitigated by having physical therapy and/or occupational therapy staff present at all additional therapy sessions beyond our current 7 day standard. The risk of dehydration will be mitigated by frequent daily phone contact by a highly-qualified nurse practitioner in the postoperative outpatient setting. Standard protocols as detailed above will be in place to protect patient PHI.

Patients in the study will benefit from increased and standardized physical and occupational therapy services in the postoperative setting, potential for improved pain control through the use of multimodal therapy, and increased preoperative and postoperative outpatient support by a highly-qualified service-specific nurse practitioner.

Decreased length of hospital stay and increased support (as detailed above) may prove to reduce the rate of overall complications and will allow patients return home quicker. Additional benefit may come in the form of reduced overall cost of care.

#### **5.4 Method for Assigning Subjects to Treatment Groups**

Patients will be randomized at the end of their operation by calling a study coordinator who will open envelopes in sequential number with treatment group detailed inside. Treatment group will be randomly sealed in envelopes prior to study initiation.

#### **5.5 Preparation and Administration of Study Drug/Therapy**

N/A, interventions as described above

#### **5.6 Subject Compliance Monitoring**

Compliance will be monitored during the patient's inpatient hospital stay and by daily phone calls on the first two days out of the hospital and all subsequent follow-up visits.

#### **5.7 Prior and Concomitant Therapy**

- N/A

## 5.9 Blinding of Study Drug

Unblinded study

## 5.10 Receiving, Storage, Dispensing and Return

## 6.0 STUDY PROCEDURES

### 6.1 Study Visit Schedule

Visit 1: If patient deemed surgical candidate, enrollment offered

Visit 2: Hospital stay, details as above. Follow-up thereafter is per post-surgical routine

## 7.0 STATISTICAL PLAN

### 7.1 Sample Size Determination

The primary outcome is the proportion of patients discharged on postoperative day 5. Group sample sizes of 71 in group one (standard pathway) and 71 in group two (intervention arm) achieve 80% power to detect a difference between the group proportions of 0.20 (for patients discharged on postoperative day 5). The proportion in group two (intervention arm) is assumed to be 0.10 under the null hypothesis and 0.30 under the alternative hypothesis. The proportion in group one (the control group) is assumed to be 0.10 (the proportion in historical data is approximately 0.09). The test statistic used is the two-sided Fisher's Exact test. Power was calculated via simulation assuming an alpha of 0.05 spent between the interim and final analysis using an O'Brien-Fleming spending function as outlined below. In simulation of 100,000 trials, if the true rate in the intervention group is 0.30, the study stopped early for efficacy 16.2% of the time.

### 7.2 Statistical Methods

Baseline demographic variables will be summarized by randomization arm using means and standard deviations (for continuous variables) or frequencies and percentages (for categorical variables), as appropriate.

#### Primary Outcome:

Randomization arms will be compared with respect to the primary outcome, proportion of patients discharged on postoperative day 5 using Fisher's Exact test. One interim analysis for efficacy will be performed when 72 patients have been randomized and completed follow-up for the primary outcome. The study will stop for efficacy if the p-value of the Fisher's exact test is less than 0.00506 at the interim analysis. Assuming the efficacy bound is not met, the null hypothesis will be rejected at the final analysis if the p-value is less than 0.04553.

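### Fisher's exact test is valid for the primary outcome but leaves alpha unused; Boschloo's exact test at the final analysis would add about 1.3 to 3.5 points of power with the same patients

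*Combined protocol and SAP*

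**What the plan says.** Section 7.2 (Primary Outcome) compares the arms on the "proportion of patients discharged on postoperative day 5 using Fisher's Exact test". There is a single efficacy look, once 72 patients have their primary outcome, with stopping at p<0.00506; otherwise the null is rejected at the end at p<0.04553.

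Section 7.1 agrees: "The test statistic used is the two-sided Fisher's Exact test". It gives the size ("Group sample sizes of 71 in group one (standard pathway) and 71 in group two (intervention arm) achieve 80% power"), the control rate ("The proportion in group one (the control group) is assumed to be 0.10 (the proportion in historical data is approximately 0.09") and the intervention rate ("assumed to be 0.10 under the null hypothesis and 0.30 under the alternative hypothesis"). The power comes from a simulation "assuming an alpha of 0.05 spent between the interim and final analysis using an O'Brien-Fleming spending function", with early stopping in 16.2% of trials under the alternative.

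Section 5.4 describes numbered sealed envelopes. It mentions no blocks and no fixed arm totals. The documents do not report the attained type I error and do not discuss another exact test.

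**The concern.** Fisher's test treats the total number of day-5 discharges as fixed. Here that total is random, whatever the arm sizes turn out to be. With about 10% events the conditional distribution has few possible values, so the attainable p-values jump past the bound and part of the 5% is never used.

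Boschloo's test ranks tables by Fisher's p-value, then asks how often a value that small arises over all tables, at the least favourable common rate. Fisher's p is at most its nominal level within every total, so it is also at most that level overall. Boschloo's p can therefore never exceed Fisher's: every table that Fisher rejects, Boschloo rejects too.

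At stake is power that needs no extra patients. The design sits close to its target (80.3% against 80%). The Study Summary and Section 4.4 give 138 patients, which is 69 per arm, where Fisher falls just short.

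**Working it through.** **Inputs.** From 7.1 and 7.2: two-sided test, rates 0.10 and 0.30, 71 per arm, bounds 0.00506 and 0.04553. Interim at 36 per arm (7.2, Safety, gives 36 per group for the 72 patients). No loss of outcome data (7.3). The unequal splits are my assumptions, since the documents give none.

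**Formulas.** Let b(x; n, p) be the binomial probability, and let R1 and R2 be the sets of tables rejected at the interim and the final look.

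- Fisher p: with the event total fixed, the sum of hypergeometric probabilities no larger than that of the observed table.
- Boschloo p: the maximum over π of Σ b(x; n1, π)·b(y; n2, π), summed over tables whose Fisher p is no larger than the observed one. The maximum was taken over 999 values of π.
- Probability of rejection: P(interim table in R1) + P(interim table not in R1 and final table in R2), summed exactly over all tables. Setting both rates to 0.10 gives the type I error; 0.10 and 0.30 give power.

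**The plan's own figures.** Fisher at 36/36 then 71/71: early stop 16.3% (plan 16.2%), power 80.3% (plan 80%). Both reproduce. The same enumeration gives a type I error of 2.07% at a common rate of 0.10, 1.98% at 0.09, and at most 3.67% at any common rate.

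**Final test changed to Boschloo at p<0.04553, Fisher interim kept.** Splits are control/intervention; all values are per cent. Size is at 10%/10%; the maximum is over all common rates.

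| Interim | Final | Fisher size | Fisher power | Boschloo size | Boschloo max size | Boschloo power | Gain |
|---|---|---|---|---|---|---|---|
| 36/36 | 71/71 | 2.07 | 80.33 | 3.50 | 4.54 | 83.81 | 3.48 |
| 36/36 | 69/69 | 2.42 | 79.22 | 3.43 | 4.59 | 82.50 | 3.28 |
| 36/36 | 70/72 | 3.23 | 82.52 | 3.77 | 4.55 | 84.31 | 1.79 |
| 36/36 | 72/70 | 3.23 | 83.87 | 3.77 | 4.55 | 85.14 | 1.27 |
| 35/37 | 69/73 | 3.17 | 84.28 | 3.80 | 4.62 | 85.90 | 1.62 |
| 37/35 | 73/69 | 3.17 | 82.04 | 3.80 | 4.62 | 84.54 | 2.50 |
| 32/40 | 66/76 | 3.30 | 82.58 | 4.10 | 4.60 | 84.44 | 1.86 |
| 36/36 | 67/75 | 3.13 | 82.26 | 4.10 | 4.53 | 85.35 | 3.09 |
| 36/36 | 75/67 | 3.13 | 83.40 | 4.10 | 4.53 | 85.11 | 1.71 |

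The two bounds add to 0.00506 + 0.04553 = 0.05059, so simple addition does not prove control at 5%. The enumeration shows it in every split run.

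**Are the bounds the cause?** Only in small part. For a normally distributed statistic they spend about 4.75% overall. With Lan-DeMets O'Brien-Fleming bounds at information 72/142 (about 0.0059 and 0.0477) and 71 per arm, Fisher has type I error 2.6% and power 81.0%. Boschloo at both looks has power 84.6%, a gain of 3.6 points.

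**Tables that change verdict at 71 per arm.** 6 v 15: Fisher p=0.057, Boschloo p=0.039. 8 v 18: 0.049 and 0.036. At 7 v 16 neither test rejects (0.067 and 0.053).

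**The case against.** The strongest reply is that nothing here is wrong. Fisher's test controls type I error, is named consistently in 7.1 and 7.2, and was the test used in the simulation. Its conservatism is already paid for in the 71 per arm. That stands in full. A reader might infer that the trial is underpowered or its primary test invalid; the documents do not support that.

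Second, a reader might take 2% as the true type I error and 3.5 points as the gain in general. Both belong to exact balance, where mirror-image tables tie and two-sided Fisher is unusually conservative. Moving one patient between arms (70/72) lifts Fisher's size to 3.2% and cuts the gain to 1.8 points. Section 5.4 does not secure equal arms, so the range is the honest figure. This stands.

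Third, the change is not free. It needs an amendment. Using Boschloo at the interim as well would raise early efficacy stopping at 36 per arm from 16.3% to 21.1%, an operating characteristic that 7.1 states. Changing the final test alone avoids this and gives up almost nothing (83.8% against 83.9% at 71 per arm).

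Fourth, Boschloo is not the only candidate. It leaves alpha unused too, and Barnard's test with a pooled z ordering, used at both looks, reaches 85.3%. That is true. Boschloo's advantage is that it rejects every table Fisher rejects, so the sponsor cannot lose by changing.

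**Conclusion.** The point holds as an efficiency gain. At the plan's bounds and 10% v 30%, Boschloo at the final analysis adds 3.5 points at 71 per arm, 3.3 at 69 per arm, and 1.3 to 3.1 in the seven unequal splits of 142 patients. Joint type I error peaks between 4.5% and 4.6%. The chance of stopping at the interim is the same under either final test: 16.3% with 36 per arm, somewhat different if the interim arms are unequal.

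This rests on the plan's rates, complete outcome data, an interim at 72 patients, and the splits listed.

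A reader might also infer that the plan will often turn real benefits into negative results. The tests disagree only for tables between the two critical regions, which under the alternative is about 3.5% of trials at exact balance and fewer in the unequal splits checked.

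**What to change.** In 7.1 and 7.2, name the two-sided Boschloo exact unconditional test for the final analysis, keeping p<0.04553. Keep Fisher's test at p<0.00506 for the interim. Report Fisher's p at the end as supportive. Rerun the simulation with the allocation method actually used, confirm that joint type I error stays below 5%, and restate power (83.8% at 71 per arm; 82.5% if 69 per arm is the intended size).

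Make the change by amendment before anyone has seen unblinded comparative data. If that point has passed, leave Fisher as the primary test and show Boschloo as a sensitivity analysis.

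The cost is an amendment, one simulation rerun and a less familiar test; no patients, visits or data are added. If the sponsor prefers Boschloo at both looks, the 16.2% early-stopping figure in 7.1 must be restated as about 21%.

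### The efficacy cuts 0.00506 and 0.04553 spend about 0.0475, not the stated 0.05, and match neither standard O'Brien-Fleming boundary; the gap is small and conservative

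*Combined protocol and SAP*

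**What the plan says.** Section 7.1 (Sample Size Determination) sets the error budget: power was simulated with "an alpha of 0.05 spent between the interim and final analysis using an O'Brien-Fleming spending function". It also fixes the test: "The test statistic used is the two-sided Fisher's Exact test". The design figures are "Group sample sizes of 71 in group one (standard pathway) and 71 in group two (intervention arm) achieve 80% power", with 0.10 assumed in the control arm and, in the intervention arm, a proportion that "is assumed to be 0.10 under the null hypothesis and 0.30 under the alternative hypothesis". The simulated chance of stopping early for efficacy under the alternative is given as 16.2%, from 100,000 trials.

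Section 7.2 (Primary Outcome) gives the rule itself. On timing: "One interim analysis for efficacy will be performed when 72 patients have been randomized and completed follow-up for the primary outcome". The trial stops if Fisher's p is below 0.00506 at that look. If it does not stop, "the null hypothesis will be rejected at the final analysis if the p-value is less than 0.04553". The Safety part of Section 7.2 confirms 36 patients per group at the interim.

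The documents do not name the O'Brien-Fleming version, state the information fraction, show how either cut was obtained, or say that any alpha was deliberately left unspent.

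**The concern.** A two-look design that spends 0.05 should have cuts whose joint crossing probability under the null is 0.05. With an interim cut as small as 0.00506 near the halfway point, little alpha is used early, and the final cut should stay close to 0.048. A final cut of 0.04553 looks too low for that interim cut.

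At stake is the primary decision rule. A few final tables would be positive at a cut that spends the stated 0.05 and are negative at 0.04553. A report that repeats the Section 7.1 description would also misstate the alpha spend.

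**Working it through.** **Inputs.** Overall two-sided alpha 0.05; 71 per arm, 142 in total; rates 0.10 and 0.30; two-sided Fisher test (all Section 7.1). Interim at 72 patients, 36 per arm; cuts 0.00506 and 0.04553 (Section 7.2). Information fraction t = 72/142 = 0.507. The second stage adds 71 − 36 = 35 per arm.

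**Step 1: reproduce the plan's own figures.** Enumerate every pair of binomial counts at 36 per arm, remove those with Fisher p < 0.00506, add 35 per arm to the rest, and apply p < 0.04553 at 71 per arm. At 0.10 v 0.30:
- Early stopping: 0.1632. The plan says 16.2%. The simulation standard error is √(0.163 × 0.837 / 100,000) = 0.0012, so these agree.
- Rejection at the final look: 0.6402.
- Power: 0.1632 + 0.6402 = 0.8033. The plan says 80%.

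The design has therefore been read as the plan intends.

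**Step 2: alpha spent by the stated pair.** Take (Z1, Z2) as bivariate normal with correlation √t = √0.507 = 0.712.
- z1 = Φ⁻¹(1 − 0.00506/2) = 2.803
- z2 = Φ⁻¹(1 − 0.04553/2) = 2.000
- P(|Z1| > z1 or |Z2| > z2) = 0.0475

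Of this, 0.0051 is spent at the interim and 0.0475 − 0.0051 = 0.0424 at the end. The shortfall against the stated level is 0.05 − 0.0475 = 0.0025. The total is also 0.0475 at t = 0.50. At t = 72/138 = 0.522 it is 0.0474, so the 138 patients in the Study Summary do not explain the gap.

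**Step 3: pairs that do spend 0.05 at t = 0.507.**
- Classical O'Brien-Fleming (cuts c/√t and c, with c solved for a total of 0.05): c = 1.978 and c/√t = 2.778, giving 0.0055/0.0479.
- Lan-DeMets O'Brien-Fleming (interim spend 4[1 − Φ(2.241/0.712)]): 0.0033/0.0489.
- Interim kept at 0.00506 and final solved for a total of 0.05: 0.0481.

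A scan over t from 0.30 to 0.79 did not produce the stated pair either. It covered the classical boundary, Lan-DeMets, and the form with interim spend 2 − 2Φ(1.96/√t). A final cut near 0.0455 needs t of about 0.60 to 0.70, where the interim cut would be 0.011 to 0.015. A plain Bonferroni split does not fit: 0.00506 + 0.04553 = 0.0506.

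**Step 4: exact operating figures of the two-stage Fisher rule.**

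| Cuts | Type I error, 10% v 10% | Maximum over common rates | Early stop, 10% v 30% | Power, 10% v 30% |
|---|---|---|---|---|
| 0.00506 / 0.04553 | 0.021 | 0.037 | 16.3% | 80.3% |
| 0.00506 / 0.0481 | 0.026 | 0.037 | 16.3% | 81.0% |

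A pair that spends the full nominal 0.05 still has exact size 0.026 at 10% rates, and the same maximum. Most of the distance from 0.05 is therefore due to Fisher's test.

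**Step 5: where the cuts sit among attainable p-values.**
- 36 per arm, 0 v 8 events: p = 0.005056, which rounds to 0.00506. The strict inequality includes this table.
- 71 per arm, 3 v 11 events: p = 0.045532, which rounds to 0.04553. The strict inequality excludes this table, because the unrounded value is slightly larger.

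Admitting 3 v 11 and its mirror images alone moves exact size at 10% v 10% from 0.021 to 0.025. Tables at 71 per arm that are negative at 0.04553 but positive at 0.0481 include 3 v 11 (0.0455), 11 v 22 (0.0459), 5 v 14 (0.0464) and 17 v 29 (0.0480).

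**The case against.** The strongest reply is that nothing harmful follows. The rule is pre-specified, numeric and unambiguous. Type I error is below 0.05 everywhere, the stated power and early stopping are met, and the whole gain from correction is 81.0% − 80.3% = 0.7 points of power. Worst-case exact size stays at 0.037 either way. All of this stands, and it limits the importance of the point. It does not make the alpha statement correct.

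A second reply is that both cuts coincide with attainable Fisher p-values at exactly the planned sample sizes, so they may have been read off the discrete distribution and normal theory is the wrong yardstick. That origin is plausible, but it is an inference; the documents do not say so. Nor would it rescue the statement that 0.05 is spent, since exact type I error is at most 0.037. It would explain why the pair fits no normal-theory boundary, and it makes the handling of the 3 v 11 table look like an accident of rounding.

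Three stronger readings are tempting and not supported:
- A reader might infer that no O'Brien-Fleming version could give this pair. Only the standard versions were checked. The plan names none, so an undocumented variant cannot be excluded.
- A reader might blame the cuts for the whole gap between 0.021 and 0.05. Step 4 shows that they account for only a small part of it.
- A reader might take the term spending function to require the Lan-DeMets pair. Its interim cut gives 14.4% early stopping, which does not fit the plan's 16.2%; a cut near 0.005 does.

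**Conclusion.** The point holds as an inconsistency between Sections 7.1 and 7.2. The stated cuts spend about 0.0475 on the nominal scale against the stated 0.05, and they match neither the classical nor the Lan-DeMets boundary at 72/142. The final test is slightly stricter than described. The practical effect is confined to a few final tables with p between 0.04553 and 0.0481, and to about 0.7 points of power. It is not a case of inflated error or of an underpowered trial.

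The result assumes the usual bivariate normal approximation for nominal alpha, an interim at exactly 36 per arm, and a final analysis at 71 per arm. It is insensitive to whether the total is 142 or 138.

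**What to change.** Choose one of two changes in Section 7.2, and align Section 7.1 with it:

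1. Preferred: keep the interim cut at 0.00506, which fits the plan's 16.2% early stopping, and set the final cut to 0.0481. The pair then spends the stated 0.05 on the nominal scale. Power becomes about 81.0%, and tables such as 3 v 11, 5 v 14, 11 v 22 and 17 v 29 become positive. The early-stopping figure needs no change.
2. If 0.04553 is kept, restate the overall nominal level as about 0.0475 and say whether a p-value equal to the attainable 0.045532 (3 v 11) is meant to reject.

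In either case, name the O'Brien-Fleming version, give the information fraction (72/142), and show how the two cuts were derived.

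The cost is SAP wording and, for the first option, one rerun of the existing simulation. No change in sample size or interim timing is needed. The first option loosens the final cut, so it should be adopted only before outcome data by arm have been seen; after that, the second is the credible choice.
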